To evaluate the efficacy of a group-based yoga intervention for urinary incontinence in ambulatory middle-aged and older women and explore potential mediators of intervention effects in this population.

Study Design

Randomized, multicenter, parallel-group trial of a 12-week yoga intervention versus non-specific muscle stretching/strengthening control intervention for ambulatory women aged 45 years and older with urinary incontinence.

Sample Size and Population

Two hundred fifty women aged 45 years and older who document stress-, urgency-, or mixed-type incontinence occurring at least once per day, are not participating in other organized yoga or muscle stretching/strengthening activities, are temporarily willing to forgo other established clinical treatments for incontinence, and meet minimum mobility and other clinical eligibility criteria, recruited from multiple locations in northern California.

Interventions and Duration

Participants will be randomized in a 1:1 ratio to participate in either a 12-week yoga program (N~120) or a time-equivalent non-specific muscle stretching/strengthening control program (N~120). Women randomized to the yoga program will take part in twice weekly group yoga classes focusing on Iyengar/alignment-based yoga techniques and practice yoga at home for at least one hour per week for 12 weeks. Women randomized to the control program will take part in twice weekly group classes focusing on non-specific muscle stretching/strengthening exercises and practice these exercises at least one hour per week at home for 12 weeks.

Study Outcomes

The primary outcome is change in the frequency of any urinary incontinence episodes between baseline and 12 weeks, measured using validated voiding diaries. Secondary outcomes include changes in the frequency of stress-type, urgency-type, daytime, and nighttime incontinence episodes (also measured by voiding diaries), as well as changes in incontinence-related functioning or quality of life (measured by validated questionnaires), between baseline and 12 weeks. Additional secondary outcomes include persistence of changes in incontinence frequency and condition-specific quality of life 12 and 24 weeks after the end of the intervention programs.

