3. STUDY DESIGN

This is a randomized, multicenter, parallel-group trial to determine whether a 12-week group-based yoga intervention is effective in decreasing the frequency and impact of urinary incontinence in middle-aged and older women. Women aged 45 years and older who document at least daily episodes of stress-, urgency-, or mixed-type incontinence on a screening voiding diary, are not using other clinical treatments for incontinence, and meet minimum physical mobility requirements and other eligibility criteria will be recruited from multiple locations in northern California by coordinators affiliated with the University of California San Francisco or Stanford University. Eligible women will be randomized in a 1:1 ratio to participate in either a 12-week yoga program (N~120) or a time-equivalent, non-specific muscle stretching and strengthening control program (N~120).

Women randomized to the yoga program will take part in twice weekly group yoga classes involving an expected 8 to 12 other women as well as practice study-specific yoga techniques at home for at least one hour per week for a total of 12 weeks. Women randomized to the muscle stretching and strengthening (a.k.a physical conditioning) control group will take part in twice weekly group physical conditioning classes and practice physical conditioning exercises at least one hour per week at home for 12 weeks. During the 12- and 24-week post-intervention follow-up period, participants will also be encouraged to continue practicing yoga or stretching/strengthening exercises for at least two hours per week.

To address objective 1, we will use validated voiding diaries to examine changes in frequency of total incontinence during the 12-week intervention, as well as explore persistence of effects on incontinence frequency after the end of the intervention programs. To address objective 2, we will further examine changes in frequency of different clinical types of incontinence as well as daytime and nighttime incontinence during the 12-week intervention, as well as the post-intervention follow-up periods. To address objective 3, we will analyze data from validated questionnaires in order to examine changes in incontinence-related functioning and quality of life over these same time periods. To address objective 4, we will assess changes in pelvic floor strength assessed during pelvic exam, autonomic

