9.5 Outcomes

9.5.1 Primary Efficacy Outcome

The primary efficacy outcome will be change in the average frequency of any urinary incontinence over 12 weeks based on a validated 3-day voiding diary. To that end, frequency of incontinence will be assessed based on voiding diaries completed at screening/baseline, 6 weeks, and 12 weeks. If improvement in incontinence is observed over 12 weeks, additional analyses may explore persistence of benefits 12 and 24 weeks after the completion of the yoga or stretching/strengthening programs.

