9.6 Data Analyses

9.6.1 Analyses to address main objectives

Objective 1: To determine the efficacy of a group-based yoga intervention in reducing the frequency of urinary incontinence in ambulatory midlife and older women.

Hypothesis 1A: Ambulatory incontinent women randomized to the yoga intervention will demonstrate at least a 20% greater decrease in total incontinence frequency (measured by validated voiding diaries) over 12 weeks, compared to women randomized to the control intervention.

Hypothesis 1B: If improvements in total incontinence frequency are observed at 12 weeks, these improvements will be sustained 12 and 24 weeks after the end of the intervention programs.

Planned analyses: Intervention effects on the primary outcome of total incontinence frequency will be estimated using a linear mixed model (LMM) for changes since baseline in the overall frequency of any incontinence episodes at 6 and 12 weeks, adjusting for baseline incontinence frequency. Analyses will be by intention to treat, according to intervention group assignment, and without regard to adherence to intervention classes or practice. The LMM will account for clustering using nested random effects for group intervention class series and individual participant. In addition to fixed effects for study location and type of incontinence, the LMM will include terms for intervention, time, and the time-by-intervention interaction, thus allowing for secular trends in controls, as well as different intervention effects at 6 and 12 weeks. The intervention effect will be summarized by an orthogonal contrast capturing any linear trend across 6 and 12 weeks; this makes use of information for participants with 6 but not 12 week outcomes. If the yoga intervention appears effective over 12 weeks, we will also assess maintenance of effects over time, by comparing changes since baseline at 12 weeks with those at 24 and 36 weeks, using an additional LMM. Intervention effects will again be summarized by an orthogonal contrast for linear trend across the three time points.

Objective 2: To determine the efficacy of a group-based yoga intervention in reducing the frequency of type- and context-specific urinary incontinence in ambulatory middle-aged and older women.

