Hypothesis 2A: Ambulatory incontinent women randomized to the yoga intervention will report decreases in the frequency of stress-type, urgency-type, daytime, and nighttime incontinence (also measured by voiding diaries) over 12 weeks, compared to women randomized to the control intervention.

Hypothesis 2B: If improvements in stress-type, urgency-type, daytime, and nighttime incontinence frequency are observed at 12 weeks, these improvements will be sustained 12 and 24 weeks after the end of the intervention programs.

Planned analyses: For additional confirmation of effects on the primary outcome of total incontinence frequency, we will examine effects on frequency of urgency

incontinence episodes and stress incontinence episodes, again using the modeling approach indicated above. Additional models will explore effects on frequency of daytime and nighttime incontinence.

Objective 3: To determine the efficacy of the yoga intervention in improving incontinence-related functioning and quality-of-life.

Hypothesis 3A: Ambulatory incontinent women randomized to the yoga intervention will report greater improvements in condition-specific functioning and quality of life (assessed by validated questionnaires) over 12 weeks, compared to women randomized to the control intervention.

Hypothesis 3B: Compared to women randomized to the control intervention, we hypothesize that women randomized to the yoga intervention will report sustained improvements in condition-specific quality of life 12 and 24 weeks after the end of the intervention programs.

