Planned analyses: Additional LMMs will examine other secondary outcomes including incontinence-related quality of life as assessed by validated questionnaires (i.e., the Incontinence Impact Questionnaire (IIQ), Urogenital Distress Inventory (UDI), Patient Perception of Bladder Condition (PPBC), Pelvic Organ Prolapse/Incontinence Sexual Questionnaire, and IUGA-Revised (PISQ-IR) questionnaire), as well as depression and anxiety symptoms assessed by additional questionnaires (i.e., the Center for Epidemiology Studies Depression Scale (CES-D), Hospital and Anxiety Depression Scale (HADS), and State Trait Anxiety Inventory (STAI)). We will again estimate intention-to-treat intervention effects, adjusting for study location, using the same modeling strategy as for objective 1. Transformation or categorization of questionnaire scores (in combination with logistic or proportional odds models) will be considered as needed to deal with skewness of outcomes.

Objective 4: To explore whether the yoga intervention is associated with improvements in 1) pelvic floor muscle strength, 2) peripheral autonomic function, and/or 3) lower extremity physical function, and assess whether improvements in these factors may mediate improvement in incontinence.

Hypothesis 4A: Among ambulatory incontinent women enrolled in this trial, the yoga intervention will be associated with improvements in a) pelvic floor muscle strength (assessed by pelvic exam), b) cardiac autonomic function (assessed by heart rate variability and impedance cardiography), and c) lower extremity physical function (assessed by physical performance assessment) over 12 weeks.

Hypothesis 4B: Among ambulatory incontinent women enrolled in this trial, changes in incontinence frequency over 12 weeks will be partly mediated by changes in a) pelvic floor muscle strength, b) cardiac autonomic function, and c) lower extremity physical function.

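### The maintenance analysis names only a linear-trend contrast, which does not give the yoga-control difference remaining at week 24 or week 36

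*Combined protocol and SAP*

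**What the plan says.** Section 9.6.1 (Objective 1, planned analyses) assesses maintenance, if yoga appears effective over 12 weeks, "by comparing changes since baseline at 12 weeks with those at 24 and 36 weeks, using an additional LMM". The next sentence names the summary: "Intervention effects will again be summarized by an orthogonal contrast for linear trend across the three time points". No contrast weights are given.

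Objectives 2 and 3 inherit the method. Stress-type and urgency-type episodes are analysed "again using the modeling approach indicated above", and the quality-of-life outcomes "using the same modeling strategy as for objective 1".

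The hypotheses are worded differently. 1B and 2B say that 12-week improvements, if seen, will be sustained. 3B carries no such condition and is comparative: "Compared to women randomized to the control intervention, we hypothesize that women randomized to the yoga intervention will report sustained improvements".

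The status of persistence also varies. The Précis lists among the secondary outcomes "persistence of changes in incontinence frequency and condition-specific quality of life 12 and 24 weeks after the end of the intervention programs". Section 3 says the trial will "explore persistence of effects on incontinence frequency after the end of the intervention programs", and section 9.5.1 says: "If improvement in incontinence is observed over 12 weeks, additional analyses may explore persistence of benefits". None of these places names an estimate at week 24 or week 36.

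**The concern.** A trend contrast describes how the treatment effect changes between visits. It does not describe how large the effect is at any one visit. A reader of the follow-up results wants to know whether women in the yoga arm are still better off than controls three and six months after classes end, and by how much. The named summary does not say.

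Two consequences follow. For quality of life, the only named summary is not the quantity that Hypothesis 3B claims. For every outcome, a non-significant trend could be presented as evidence that benefit was maintained, although the contrast would usually miss a substantial loss. The plan does not propose that reading, but does not rule it out.

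Prespecification matters here because sections 6.2.4 and 9.3 unblind the study once the 12-week dataset is complete. That can happen before 36-week follow-up ends, so follow-up estimates not named beforehand could be chosen with knowledge of allocation.

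**Working it through.** **What the contrast estimates.** Write d12, d24 and d36 for the yoga-control difference in reduction (episodes/week, benefit positive). Weeks 12, 24 and 36 are equally spaced, so the standard linear weights are (-1, 0, +1) and the contrast is d36 - d12.

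| Pattern (d12, d24, d36) | Contrast |
|---|---|
| 4.7, 4.7, 4.7 (all kept) | 0 |
| 1, 1, 1 (small effect, kept) | 0 |
| 4.7, 0, 4.7 (lost, then regained) | 0 |
| 4.7, 2.35, 2.35 (half lost by week 24) | -2.35 |
| 4.7, 4.7, 2.35 (half lost after week 24) | -2.35 |
| 4.7, 4.7, 0 (all lost) | -4.7 |
| 9.4, 7.05, 4.7 (4.7 remains) | -4.7 |

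The same contrast value is compatible with very different remaining effects, so it fixes neither d24 nor d36.

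**Inputs.** Section 9.2: baseline 23-24 episodes/week, 20% difference (4.6-4.8; 4.7 used), SD of change 14.4, correlation of outcome values 0.59, 120 per arm, 15% loss by 3 months. Section 9.6.2: loss below 20% at week 24 and below 25% at week 36. Taking those limits, 120 × 0.85 = 102, 120 × 0.80 = 96 and 120 × 0.75 = 90 per arm.

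**The plan's own figure.** The total of 240 is approximately reproduced with adjusted SD 14.4 × √(1 - 0.59²) = 11.63 and difference 4.6. Then n = 2 × (1.96 + 0.84)² × 11.63² / 4.6², giving 101 per arm; 101/0.85 gives 119, or 238 in total. This treats 14.4 as the SD of the outcome, although the text calls it the SD of change. Both readings are carried below. No figure is given for the maintenance analysis.

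**Assumptions added here.** Correlation 0.59 between any two visits, no class clustering, and loss of half the benefit (2.35) as a benchmark. The plan sets none of these for follow-up.

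**Reading A: 14.4 is the SD of change.**
- Outcome SD = 14.4/√(2 × 0.41) = 15.90
- Contrast: SE = 14.4 × √(2/90) = 2.15; half-width 1.96 × SE = 4.21; power for 2.35 = 19.5%
- Baseline-adjusted SD = 15.90 × √(1 - 0.59²) = 12.84
- d36: SE 1.91, half-width 3.75, power 69.0% if 4.7 remains and 23.3% if 2.35 remains
- d24 (96 per arm): SE 1.85, half-width 3.63, power 71.8% if 4.7 remains

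**Reading B: 14.4 is the outcome SD.**
- SD of the week 12 to 36 change = 14.4 × √0.82 = 13.04
- Contrast: SE 1.94, half-width 3.81, power for 2.35 = 22.7%
- Baseline-adjusted SD = 11.63
- d36: SE 1.73, half-width 3.40, power 77.4% if 4.7 remains and 27.3% if 2.35 remains
- d24: SE 1.68, half-width 3.29, power 80.0% if 4.7 remains

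The contrast half-width is therefore 81% (3.81/4.7) to 90% (4.21/4.7) of the target effect. Baseline adjustment does not change its SE under equal correlations.

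**Using all women seen.** A generalised least squares calculation with 102, 96 and 90 per arm and monotone loss gives contrast half-widths of 4.12 (A) and 3.73 (B), half-loss power of 20.1% and 23.5%, and d36 power of 69.9% and 78.2%. Little changes.

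**Sensitivity.** With correlation 0.4 to 0.8, half-loss power stays at 19.5% under A and runs from 17.0 to 41.0% under B. If 0.59 instead applied to baseline-adjusted values with SD 11.63, it would be 32%, with half-width 3.08.

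**The case against.** The strongest reply is that nothing is lost except a line of reporting. The primary model has time-by-intervention terms. If the additional model keeps them, it yields d24 and d36 directly, and nothing says they will be withheld. For 1B and 2B, asking whether an improvement was sustained is a question about change after week 12, which d36 - d12 addresses. The sentence before the named summary already compares week 12 with both later visits, which would separate early from late loss. The (-1, 0, +1) weights are inferred. Persistence of incontinence frequency is conditional and described as exploratory.

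Much of this stands. The gap is in what will be reported, not in what can be estimated; the substantive mismatch is sharpest for 3B; and the weights are the ordinary reading rather than stated text. But comparing week 12 with weeks 24 and 36 still describes change, not the difference that remains. Adding the contrast to d12 would recover d36 only if d12 were reported, and the primary analysis too is summarised by a linear trend; d24 would still be missing.

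A second reply is that the power figures are fragile. Only Reading B comes close to the planned sample size: Reading A's adjusted SD of 12.84 would need 266 to 290 women. If 0.59 referred to baseline-adjusted values, the contrast would be more precise (half-width 3.08) than d36 (3.40). That is fair, so greater precision is not the main argument for the change. Section 9.2 attaches 0.59 to outcome values, however, and even at 32% power about two in three half-losses would go undetected.

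**Conclusion.** The concern holds. The only summary named for maintenance estimates change in the effect after week 12, and no section plans to report the yoga-control difference at week 24 or week 36. Hypothesis 3B needs that difference; 1B, 2B and the persistence outcome need it for interpretation.

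Under the stated assumptions, the contrast detects loss of half the benefit with only 19 to 23% power. The direct week-36 comparison has 69 to 77% power if all the benefit remains, but only 23 to 27% if half remains. The gain from the change is therefore mainly an effect stated at each visit; the gain in precision is modest and depends on the correlation structure. The power figures also rest on the reviewer's half-loss benchmark and on ignoring class clustering.

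This should be changed, but it does not touch the 12-week primary conclusion.

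**What to change.** In section 9.6.1, amend the maintenance paragraph as follows:

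- Name as the persistence summaries the between-group differences in change from baseline at week 24 and at week 36, each with a 95% CI, from the additional mixed model with time-by-intervention terms.
- Keep d24 - d12 and d36 - d12, with 95% CIs, as descriptions of decay.
- State that a non-significant trend will not be interpreted as maintenance, and that the visit-specific estimates do not by themselves prove full maintenance, because no retention margin is set.
- Apply the same wording to the outcomes under Objectives 2 and 3.

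The cost is SAP wording only. The model and data are those already planned.

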6.1.7 Pelvic Floor Muscle Strength

To guide exploration of changes in pelvic floor muscle strength as a potential mediator of intervention effects in women with incontinence, participants will be invited to undergo the following optional assessment of pelvic floor muscle strength at baseline and 12 weeks. For this assessment, a clinically-trained assessor (doctor, nurse, or pelvic floor physical therapist) will perform a digital pelvic exam and ask the participant to squeeze her pelvic floor muscles during exam. The assessor will then rate pelvic muscle strength using the Brink scale, which includes 4-point scales in 3 categories—contraction pressure, displacement of the examiner's fingers, and duration of squeeze—to create an overall score of 0 to 12.⁸⁴⁻⁹⁰ Since this is an optional assessment, participants who have a relative contraindication to pelvic exam or anticipate pain with pelvic exam can decline to undergo this measurement. During the COVID-19 pandemic, participants may also decline to undergo these measurements that require them to come into close proximity (less than 6 foot distance) with study personnel. For assessments performed after randomization, the assessor will be blinded to intervention assignment.

At the Stanford clinical site, participants will also be invited to undergo perineometer assessment of pelvic floor muscle strength by a board-certified urogynecologist at the same timepoints (baseline and 12 weeks). Participants will be asked to contract their pelvic floor muscles, and contraction strength will be measured with a Laborie Urostym digital perineometer. This device is currently used clinically and approved for pelvic floor physical therapy and biofeedback. Measurements obtained by perineometer have previously been shown to have good inter-rater and test-retest reliability. Measurements will include minimum, maximum, and average strength of each pelvic floor muscle contraction measured. Duration of contraction will also be recorded. A total of three contractions will be measured by digital perineometry. Measurements

will be recorded in cm H₂O or mm Hg. Each patient will be assigned a vaginal sensor that will be processed according to manufacturer's recommendation and used for the baseline and follow-up exams. Since this is an optional assessment, participants who have a relative contraindication to pelvic exam or anticipate pain with pelvic exam can decline to undergo this measurement.

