Planned analyses: Additional intermediary outcomes include pelvic floor muscle strength (measured by Brink scale), peripheral autonomic function (reflected by respiratory sinus arrhythmia [RSA] and cardiac pre-ejection period [PEP] parameters), and lower extremity physical function (assessed using the Short Physical Performance Battery [SBBP] and 2-minute step test). Intervention effects will first be estimated using LMMs, using the same modeling strategy used for objectives 1-3. Next, to assess for mediation of changes in incontinence frequency by changes in these factors, we will assess correlation between changes in these

parameters and change in incontinence frequency between baseline and 12 weeks. We will then examine attenuation of intervention effects estimates from the primary intention-to-treat analyses after adjustment for these potential mediators. Mediators will initially be analyzed as continuous variables (i.e., continuous change in RSA and PEP), but categorization will be considered in the event of skewed variable distributions. If evidence of mediation is observed, we will estimate 95% bias-corrected percentile confidence intervals for the proportion of intervention effect explained, using resampling by participant to fully account for the correlation between intervention effect estimates before and after adjustment for change in the mediators

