9.6.2 Other analytic issues

Participant dropout (i.e., early termination or loss-to-follow-up). Participant dropout levels are expected to be <15% at 12 weeks of intervention, <20% at 12 weeks post-intervention follow-up, and <25% at 24 weeks post-intervention follow-up, assuming a similar rate of attrition over time. The assumption of non-informative dropout will be assessed by comparing baseline characteristics and early post-randomization outcomes of dropouts vs. non-dropouts. If dropout rates differ between groups, sensitivity analyses to evaluate the effects of participant dropout on estimates of intervention effects may be run using inverse probability of retention weights, which can legitimately include post-randomization variables associated with dropout. Alternately or in addition to this, we may use multiple imputation of missing outcomes under plausible informative missingness assumptions.¹⁰⁴

Dose effects (length of exposure and intensity of practice). In the event that the primary analysis shows that yoga intervention is effective in reducing incontinence frequency over 12 weeks, we may use a closed test procedure to assess for dose response in length of intervention exposure without inflating type-I error.¹⁰⁵ Specifically, if we detect a statistically significant benefit over 12 weeks an alpha of 0.05, we may assess change from baseline to 6 weeks, and from 6 weeks to 12 weeks, also at alpha of 0.05, based on contrasts that can be obtained from the primary analysis model. In exploratory analyses, we may also examine whether cumulative hours spent in group intervention classes (based on class attendance logs), or total hours of home yoga or stretching/strengthening practice (documented by participants' home practice logs), are associated with changes in incontinence frequency or secondary outcomes in each group. After the end of the 12-week intervention, additional exploratory analyses may examine associations between continued yoga or control intervention practice (based on continued home practice hours) and maintenance of intervention effects.

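### Objective 4 compares the full intention-to-treat effect with a mediator-adjusted effect that, on a plain reading, uses only women with mediator data; this can hide real mediation and can move the proportion explained either way

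*Combined protocol and SAP*

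**What the plan says.** Objective 4 is exploratory: "To explore whether the yoga intervention is associated with improvements in 1) pelvic floor muscle strength", autonomic function or lower-extremity function, and whether these mediate improvement in incontinence. Section 9.6.1 plans three steps.

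1. Correlate changes in these "parameters and change in incontinence frequency between baseline and 12 weeks".
2. Attenuation: "We will then examine attenuation of intervention effects estimates from the primary intention-to-treat analyses after adjustment for these potential mediators".
3. An interval: "If evidence of mediation is observed, we will estimate 95% bias-corrected percentile confidence intervals for the proportion of intervention effect explained", obtained "using resampling by participant to fully account for the correlation between intervention effect estimates before and after adjustment".

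The primary model (section 9.6.1, Objective 1) covers changes at 6 and 12 weeks. Of its linear-trend summary the plan says that "this makes use of information for participants with 6 but not 12 week outcomes".

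The mediators are less complete. Section 6.1.7: "participants will be invited to undergo the following optional assessment of pelvic floor muscle strength at baseline and 12 weeks". Women may decline the Brink examination for a relative contraindication, expected pain or, during the pandemic, proximity to staff. RSA and PEP, also taken only at baseline and 12 weeks, may be declined during the pandemic (section 6.1.6) or forgone by women with a history of reaction to electrodes (section 7.1). The physical performance tests are not optional and are repeated at 6 weeks (sections 6.1.5 and 6.2.7).

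On missing data, section 9.6.2 says under participant dropout that "we may use multiple imputation of missing outcomes under plausible informative missingness assumptions".

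**The concern.** The proportion explained is one minus the ratio of an adjusted effect to an unadjusted effect. It measures mediation only if the adjustment is the sole difference between the two. Here the unadjusted effect is the primary estimate, from all women with a 6- or 12-week diary. Without imputation, the adjusted effect can use only women with paired mediator data. Part of any attenuation is then the difference between two groups of women.

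Participant resampling carries the correlation between the two estimates into the interval, as intended. It does not make them describe the same women: each resample repeats the same mismatch.

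There is reason to think that missingness may be related to response. Pandemic waves, in which measurements may be declined, are also those in which classes may be remote, and section 9.6.2 plans to examine whether the effect differs between remote and in-person waves. It also lists baseline pelvic floor strength as a possible effect modifier.

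At stake is Hypothesis 4B. The mismatch mainly concerns Brink, RSA and PEP; the performance tests are drawn in mainly through a joint model.

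**Working it through.** **Inputs from section 9.2.** Baseline 23–24 episodes/week; SD of change 14.4; correlation 0.59; 15% loss; 120 per group; 20-point difference.

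**The plan's own figure.** Residual SD = 14.4 × √(1 − 0.59²) = 11.63. Per group, 120 × 0.85 = 102. At 23 episodes/week the difference is 0.20 × 23 = 4.6, giving 80.7% power, or N = 238 for 80%. The stated 80% with 240 is reproduced. The checks below use 0.20 × 23.5 = 4.7.

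**Assumed, because the documents do not give them.** Uptake f = 50, 70, 85 or 95% (50% is more plausible for Brink than for RSA/PEP). A mediator effect of 2.82 episodes/week per SD, with the mediator shifted 0.5 SD by yoga: 0.5 × 2.82 = 1.41 = 0.30 × 4.7, a true proportion of 0.30. Evidence of mediation, which the plan does not define, is taken as a favourable mediator–outcome correlation at p < 0.05.

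**Uptake unrelated to response: noise, no systematic shift.** The SE of the full effect is 11.63 × √(2/102) = 1.63. The unadjusted effects in all women and in measured women differ by chance alone with SD 1.63 × √(1/f − 1): 1.63, 1.07, 0.68 and 0.37 episodes/week at 50, 70, 85 and 95% uptake. The indirect effect sought is 1.41.

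The simulation used 102 per arm, one 12-week outcome, least squares, no class effect, and bias-corrected percentile intervals (1000 runs × 600 resamples; Monte Carlo error up to about 3 points). Detection means that the correlation criterion is met and the interval lies above zero, among runs with a significant full effect.

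| Uptake | Different women | Same women |
|---|---|---|
| 50% | 12% | 44% |
| 70% | 19% | 63% |
| 85% | 39% | 82% |
| 95% | 61% | 88% |

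A separate simulation with a true proportion of 0.50 gave 34% against 65% at 60% measured. With random uptake, a mediator that predicts outcome and no shift by yoga, the apparent proportion exceeded 20% in 19, 15, 9 and 3% of runs against 6, 4, 2 and 1%, but the interval lay above zero in only 2–3% against 3–4%. Under random uptake the interval therefore contains the extra noise.

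**Uptake related to response: a shift.** Let r = effect in measured women / overall effect. The mixed proportion is 1 − (1 − PE) × r, with PE the true proportion (in measured women), so the shift is (1 − PE)(1 − r). If unmeasured women have k times the effect of measured women, r = 1/(f + (1 − f)k).

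| Uptake | k = 1.5: r | Shift, PE 0.30 | Shift, PE 0 | k = 0.5: r | Shift, PE 0.30 | Shift, PE 0 |
|---|---|---|---|---|---|---|
| 50% | 0.80 | +0.14 | +0.20 | 1.33 | −0.23 | −0.33 |
| 70% | 0.87 | +0.09 | +0.13 | 1.18 | −0.12 | −0.18 |
| 85% | 0.93 | +0.05 | +0.07 | 1.08 | −0.06 | −0.08 |
| 95% | 0.98 | +0.02 | +0.02 | 1.03 | −0.02 | −0.03 |

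- *Measured women respond more (k = 0.5; indirect effect held at 1.41):* detection is 1, 7, 22 and 53% against 49, 71, 82 and 90% in the same women.
- *Measured women respond less, real mediation (k = 2, true proportion 0.30):* 34% against 28% at 50% uptake and 52% against 53% at 70%. Little or nothing is hidden.
- *Measured women respond less, no mediation (mediator predicts outcome, yoga does not shift it):* at k = 1.5 and 50, 70 and 85% uptake, the interval lies above zero in about 6, 8 and 5% of runs against 2–3%, and the apparent proportion exceeds 20% in 31, 32 and 18% against 8, 5 and 3%. At k = 2 the interval lies above zero in 10–14% against about 4%. Over repeated runs at k = 1.5 to 2 the range is about 5–16% against 1–4%.

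**The case against.** The complete-case adjusted model is inferred from silence. Nothing forbids refitting the unadjusted model in women with mediator data, and the text on estimates before and after adjustment could be read that way. Section 9.6.1 also calls the mediators intermediary outcomes, so the optional imputation of missing outcomes in section 9.6.2 might extend to them. Both points stand, and they limit the finding to what the plan says when followed as written: it names the primary estimate as the starting value, sets no common sample, and places imputation under dropout, which does not clearly cover a woman who stays in the trial but declines a measurement.

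The sizes depend on undocumented uptake, mediator strength, effect ratio and criterion, and on a significant full effect, a condition the plan does not state for step 2. That stands too, and is why ranges are shown. If the criterion also required yoga to shift the mediator, false mediation in the unfavourable case would fall to 2% or less, but the plan does not state this.

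Some stronger inferences fail. A reader might conclude that the mismatch always hides mediation, or that false mediation can be disregarded; the direction depends on who is measured. A reader might think the main result is compromised; the mediators do not enter it. And a reader might say the visit table contradicts the use of the Short Physical Performance Battery; section 6.2.7 names no individual performance tests. The mismatch is with section 6.1.5.

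**Conclusion.** The concern holds for Objective 4 as an inference from the plan's wording. If uptake is unrelated to response, the proportion is not systematically shifted, but detection falls to roughly half of the same-women figure at 85% uptake and to about a quarter at 50% (assumed true proportion 0.30). If uptake is related to response, the proportion moves down when measured women respond more and up when they respond less; in the latter case false mediation also rises. At 95% uptake the shift is only 0.02–0.03, although detection is still 61% against 88%. Women with a 6-week but no 12-week diary, a subset of the expected 15% × 240 = 36 lost by 12 weeks, widen the mismatch and were not modelled. The primary analysis and the sample size are unaffected. The change should be made because mediation has its own hypothesis and the remedy is cheap.

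**What to change.** - For each mediator, and for any joint model, fit the unadjusted and adjusted models in the same women (12-week diary plus baseline and 12-week mediator), within each participant resample already planned.
- Report N and the same-sample total effect beside the full intention-to-treat estimate.
- Add a sensitivity analysis with imputation or weighting for missing mediators, using data already collected, and say what counts as evidence of mediation.
- Brink, RSA and PEP have one post-baseline value, so the 6- and 12-week trend model cannot be used for them as written. Model the 12-week change with baseline adjustment.
- Separately, section 9.6.1 names the Short Physical Performance Battery, while section 6.1.5 lists balance tests, a 30-second chair stand and a 2-minute step test. Name the lower-extremity measures actually collected.

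Cost: a few sentences and modest programming, with no new data. The same-sample estimate is less precise, describes only measured women, and can be unstable at low uptake: in simulations where poorer responders were the ones measured, its interval coverage fell to about 81–87% at 40–60% measured. Hence the sensitivity analysis.
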